10.2.2 Replacement Policy

Because this is an open label study with limited number of patients, 14 accrued eligible patients with clinical tumor assessments and biomarkers measurements at baseline and the end of study window are required for the study. Additional patients will be enrolled to replace patients without clinical tumor assessments and completed biomarker measurements for both timepoints and at least one of the five biomarkers of interest. However, all patients will be followed and included for safety assessments.

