2.3 Endpoints

2.3.1 Primary Endpoint

- Quantitative change in the sum of RECIST-measurable index lesions on paired, pre- and post-treatment tumor measurement (ΔT) with size treated as a continuous variable.
- The difference in ΔT in patients with genomic *PIK3CA* pathway alteration (*PIK3CA* mutation, amplification, and FISH for PTEN loss) vs. no genomic activation

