10.2 Determination of Sample Size and Accrual Rate

10.2.1 Sample Size and Power Estimate

The primary objective of the study is to identify baseline and/or pharmacodynamic biomarkers that might have predictive utility to determine the clinical response to BYL719. The overall sample size is 14 evaluable patients. Accrual will continue until 14 evaluable patients have enrolled. If patient had baseline tissue samples obtained, has taken at least 10 doses of drug, and has undergone response assessment that is of sufficient quality to assess the primary clinical and biomarker endpoints, they are evaluable. Based upon prior window trials, up to 20 patients will be enrolled to meet these criteria. The sample size is based upon the following considerations: half of enrolled patients will demonstrate genomic PI3K pathway activation, defined as PIK3CA mutation or amplification, or PTEN deletion. We expect those with genetically activated PI3K to demonstrate a median Δ Tumor size of (-)20%, whereas those with no genomic PI3K activation to demonstrate a median increase of (+)5%. Alpha is set to 0.03 and beta is set to 0.20.

As a biomarker study, the statistical design is to accrue a sufficient number of patients and provide 80% power to test one or any of 5 key hypotheses with individual alphas of 0.03: 1) relationship between Δ Tumor size and baseline genomic *PIK3CA* activation; 2) relationship between Δ Tumor size and change in expression of HPV mRNA (qPCR); 3) relationship between Δ Tumor size and change in expression of E6, E7 oncoprotein (immunoblotting); 4) relationship between Δ Tumor size and change in expression of phospho-HER3 (immunoblotting and RPPA); 5) relationship between Δ Tumor size and change in expression of HER3/PI3K dimers (Monogram). 14 patients with complete biomarker data are needed to achieve 80% power for the 5 primary hypothesis and limit overall family wise error rate (FWER) to 15%. Based upon prior window trials, accounting for treatment compliance and quality paired tumor specimens, this will require enrollment of 20 patients.

As an example, to justify the sample size for the first key hypothesis (relationship between Δ Tumor size and baseline genomic *PIK3CA* activation), the standard deviation of Δ Tumor size

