Appendix 5 Tumor Biomarkers

Tumor tissues obtained before treatment with BYL719 will be assessed for canonical *PIK3CA* mutations by SNaPshot PCR(60) and amplifications by FISH.(53) *PTEN* loss will be assessed by FISH.(53) In addition, we will assess *PIK3CA* mutations using a comprehensive full length sequencing approach covering 202 cancer associated genes to ultradeep depth developed as part of the SU2C PI3K in women project.(53) We will assess HPV viral load and levels of HPV E6 and E7 transcripts in paired, pre- and post-treatment tissues by RT-qPCR. We will assess HPV viral load by qPCR and levels of HPV E6 and E7 transcripts by RT-qPCR in paired, pre- and post-treatment tissues. We will also assess paired tumor cell lysates for expression of total and phosphorylated signaling proteins using reverse phase protein array (RPPA), a high-through-put quantitative proteomics platform to detect changes in signaling events.

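### The replacement rule in 10.2.2 can fill the 14 with patients who have no PIK3CA/PTEN result, so its 14 are not the 14 that the power statement in 10.2.1 assumes

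*Combined protocol and SAP*

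**What the plan says.** Section 10.2.1 states the basis of the sample size: "14 patients with complete biomarker data are needed to achieve 80% power for the 5 primary hypothesis". The first hypothesis relates change in tumor size to baseline genomic PIK3CA activation. It is powered with a two-sample t test at 7 per group, on the expectation that "half of enrolled patients will demonstrate genomic PI3K pathway activation, defined as PIK3CA mutation or amplification, or PTEN deletion". The other four hypotheses relate change in tumor size to change in HPV mRNA, E6/E7, phospho-HER3 and HER3/PI3K dimers.

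Section 2.3.1 makes the genomic contrast a primary endpoint, with groups defined by "mutation, amplification, and FISH for PTEN loss) vs. no genomic activation". Appendix 5 gives the timing of the assay: "Tumor tissues obtained before treatment with BYL719 will be assessed for canonical" PIK3CA mutations, and it adds FISH for amplification and PTEN loss.

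Two rules decide who counts.

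- **Evaluability, 10.2.1:** "If patient had baseline tissue samples obtained, has taken at least 10 doses of drug, and has undergone response assessment". The sentence goes on to ask that this assessment be good enough for the primary clinical and biomarker endpoints. It names no genomic result.
- **Replacement, 10.2.2:** 14 patients need tumor assessments and unspecified biomarker measurements at both timepoints. A patient is replaced when lacking the tumor assessments or "completed biomarker measurements for both timepoints and at least one of the five biomarkers of interest".

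Enrollment is set at 20: "accounting for treatment compliance and quality paired tumor specimens, this will require enrollment of 20 patients".

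**The concern.** Complete data and at least one of five are different counting rules for the same 14 patients. Genomic status has no second timepoint, so only the four change-in-expression biomarkers can satisfy a both-timepoint condition. The mismatch runs in both directions:

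- A patient with paired HPV mRNA and no genomic result is not replaced, yet belongs to neither group in hypothesis 1.
- A patient with a genomic result and a measured tumor change, but no usable surgical specimen, triggers replacement, although hypothesis 1 does not need that specimen.

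Accrual could therefore close with fewer than 14 patients in a primary contrast. The plan also does not say what happens to a patient whose genomic result is missing or partial. In an open-label study of this size, that choice should not be left until tumor changes are known. Hypotheses 2 to 5 can likewise each fall short of 14 pairs.

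**Working it through.** **Inputs.** From 10.2.1: means -20% and +5% (difference 25 points), SD 8%, alpha 0.03, 7 per group, 20 enrolled for 14 evaluable. Sidedness is not stated; two-sided is used here. The number of patients without a genomic result is not in the documents. I show 0 to 4 as an assumption; 4 is about 30% of 14 (0.30 × 14 = 4.2). The documents use 30% as the loss from 20 to 14, not as a genomic failure rate. SD 12 is also an assumption.

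**Step 1: the plan's own figure.** For an equal-variance t test the noncentrality is 25 / (8 × √(1/7 + 1/7)) = 5.85 on 12 degrees of freedom, with critical value 2.46. Power is 99.9% two-sided (99.98% one-sided), which agrees with the stated figure of more than 90%. Five tests at 0.03 sum to 0.15, as stated.

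**Step 2: unclassified patients left out.** Of 7 activated and 7 not, k are missing at random and m of those k are truly activated (hypergeometric). Power is computed for (7 - m) versus (7 - k + m) and averaged over m.

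**Step 3: unclassified patients read as no genomic activation.** The groups become (7 - m) versus (7 + m), with m patients responding at -20% inside the comparator. With m = 2 the comparator mean is (7 × 5 + 2 × (-20)) / 9 = -0.6, so the difference shrinks from 25 to 19.4 points. By simulation (200,000 runs per m), power at SD 8 for m = 1, 2, 3 is about 95%, 72% and 40%. The table averages these over m.

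| Missing k | SD 8, left out | SD 8, read as negative | SD 12, left out | SD 12, read as negative |
|---|---|---|---|---|
| 0 | 99.9% | 99.9% | 90.8% | 90.8% |
| 1 | 99.7% | 97.3% | 87.7% | 80.5% |
| 2 | 99.4% | 90.8% | 83.6% | 69.4% |
| 3 | 98.7% | 81.0% | 78.4% | 58.2% |
| 4 | 97.2% | 69.0% | 72.0% | 47.5% |

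Simulated entries carry an error of about 0.1 point.

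**Step 4: how far the plan's margin reaches.** At SD 8 with a balanced split of those classified, power is 97.6% with 10, 90.7% with 8, 81.8% with 7 (3 versus 4) and 69.3% with 6. The rule in 10.2.2 sets no lower limit on this number.

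**Step 5: partial results.** Section 1.3 gives PIK3CA mutation in 27-31% and any pathway event in 45-60%. A patient who is mutation-negative but has no FISH result therefore still has a chance of activation between (0.45 - 0.31) / 0.69 = 20% and (0.60 - 0.27) / 0.73 = 45%. Such a patient cannot safely be called negative.

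**Step 6: hypotheses 2 to 5.** No test or effect size is stated, so the cost of having fewer than 14 pairs cannot be calculated from the documents.

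**The case against.** Five points can be made for the plan.

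1. **10.2.1 may already require an assessable genomic endpoint.** Accrual runs until 14 evaluable patients have enrolled, and the evaluability sentence mentions quality sufficient for the primary clinical and biomarker endpoints. That clause qualifies the response assessment; for tissue the sentence asks only that baseline samples were obtained. Even on the generous reading it would conflict with 10.2.2, so the two still need reconciling.
2. **10.2.2 is loosely drafted.** It could mean that anyone lacking any one of the five is replaced, which would agree with 10.2.1. That is possible but is not the plain reading, and it leaves genomic status with a second timepoint it does not have. The ambiguity is itself a reason to reword.
3. **The power loss may be negligible.** This largely stands. A reader might infer that the contrast falls below its 80% target. At SD 8 that requires four patients misread as negative, and no passage directs such a reading. With up to four left out, power stays above the stated 90%. The assumed count also borrows an allowance already used to go from 20 to 14. A mandatory baseline sample (6.1.3) and two mutation assays (Appendix 5) point to fewer genomic failures.
4. **Replaced does not mean excluded.** This stands. A reader might infer that a patient without paired tissue is dropped from hypothesis 1. Section 10.2.2 governs further enrollment and keeps everyone for safety ("However, all patients will be followed and included for safety assessments"). Section 7 defines evaluability for tumor change without a tissue requirement.
5. **Requiring all paired biomarkers goes too far.** It is tempting to demand complete data on all five from every counted patient. Any single assay failure would then trigger replacement, and the cap of 20 could be exhausted. This objection stands, and the fix below does not ask for it.

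**Conclusion.** The inconsistency is real and should be corrected: as written, 10.2.2 does not secure the 14 classified patients on which 10.2.1 bases the PIK3CA contrast. The consequence is modest under the plan's own assumptions, with power of 99.9% falling to 97.2% if four patients are unclassified and left out. It is material under either of two conditions, neither stated in the plan. One is that unclassified patients are placed in the no-activation group (about 91% with two, 69% with four, at SD 8). The other is a larger SD (at 12, 90.8% falling to 72% with four left out). The number missing, missingness at random, a two-sided test and SD 12 are assumptions. For hypotheses 2 to 5 the documents support only the statement that each may have fewer than the 14 that 10.2.1 says it needs.

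**What to change.** - **Counting rule (10.2.1 and 10.2.2).** Count a patient toward the 14 only with a usable baseline PIK3CA/PTEN classification and paired pre- and post-treatment tumor measurements, alongside the existing requirement of at least 10 doses. Replace others within the planned 20.
- **Contrast 1 population.** Include every patient with a tumor change and a known group, even if paired tissue failed.
- **Classification.** Activated means that any one of PIK3CA mutation, amplification or PTEN loss is found. No activation means that all three were tested and are negative. Anyone else is not classifiable, is left out of the contrast and is counted in the report, never placed in the no-activation group.
- **Hypotheses 2 to 5.** Report the number of pairs analyzed for each, and limit the statement that 14 patients give 80% power to hypotheses that reach 14 pairs.

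The cost is wording; no new assay is needed and the 2.3.1 definition is unchanged. Enrollment may run closer to 20. If genomic failures of 10% or 20% (assumed) came on top of the 30% loss, 14 / (0.7 × 0.9) = 22.2, so 23, or 14 / (0.7 × 0.8) = 25 enrolled patients would be needed. The cap of 20 would then bind, fewer than 14 would be classified, and the achieved number and power would have to be restated.

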10.3 Protocol Early Stopping Rules

10.3.1 Toxicity

A continuous monitoring rule for safety will be instituted, to guard against excess toxicity from pre-operative treatment with BYL719 at 350 mg po daily, the RP2D for this agent. All patients will be treated at the dose of BYL719 350 mg po daily. After enrollment of the 6th patient, we will continuously monitor the number of patients who discontinue BYL719 and come off study for BYL719-attributable toxicity. A qualifying toxicity must be at least possibly related to BYL719, as judged by the treating investigator, and fulfill one of the following definitions:

- Grade ≥ 3 non-hematologic toxicity, with the exception of asymptomatic electrolyte abnormalities manageable with repletion.
- Intolerable non-hematologic toxicities of any grade, which persist despite optimal medical management.
- Grade ≥ 3 thrombocytopenia or neutropenia.
- Any grade toxicity that results in a significant delay of surgery, defined as more than 42 days from the start of BYL719 protocol treatment.

If the posterior probability of $\geq 33\%$ toxicity rate exceeds 50% for patients having to discontinue window treatment due to qualifying toxicity, this would be considered unacceptable. The study would be placed on hold and would be referred to the UACC DSMB for evaluation of excess toxicity and recommendations for design change or study closure.

Table 8 below describes the number of toxicity events per number of treated patients required to trigger referral to the UACC DSMC. Table 8 also shows the posterior probability that the rate exceeds 33%, and the binomial probability associated with the decision for an assumed 33% discontinuation rate. The prior probability has a beta distributions with parameters $a = 1$ and $b = 9$, assumes a 10% mean with an approximate 80% mid-range of .0 to .22.

Table 8. Boundaries for the Excess Toxicity Rule

Subjects	Treatment-Related Discontinuations	PP($\pi > 33\%$)*	Pr($X \geq r p = .33$)
6	5	.629	.017
8	6	.685	.019
11	7	.673	.037
14	8	.664	.054
17	9	.657	.071
20	10	.650	.087

* π is the discontinuation rate. The minimum acceptable upper bound of a treatment-related discontinuation is 33%. PP($\pi > 33\%$) is the posterior probability that the discontinuation rate exceeds this 33% upper bound. This posterior probability of discontinuation is calculated from the prior distribution, the number of subjects treated and the observed number of treatment-related discontinuations.

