5.2 Dose Modification

A continuous monitoring rule for safety will be instituted, to guard against excess toxicity from pre-operative treatment with BYL719 at a starting dose of 350 mg daily.

For patients who do not tolerate the protocol-specified dosing schedule, dose adjustments are permitted in order to allow the patient to continue the study treatment. All dose modifications must be based on the worst preceding toxicity as graded by the NCI Clinical Toxicity Criteria ([NCI-CTCAE version 4.03]).

If the administration of BYL719 is interrupted for reasons other than toxicity, then treatment with BYL719 may be resumed at the same dose.

A maximum of 2 dose reductions of BYL719 from the recommended starting dose may be allowed before considering discontinuation of BYL719 treatment. Table 5.2 below describes the dose reduction steps for BYL719.

Table 5. 2 Dose reduction steps for BYL719

A single agent dose levels and dose reductions*	
Starting dose level	350 mg/day continuously
Dose level – 1	300 mg/day continuously
Dose level – 2	250 mg/ day continuously **

*Dose reduction should be based on the worst preceding toxicity.
 ** = If a dose reduction below dose level –2 is required, the patient must be permanently discontinued from BYL719

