A monitoring visit report and follow-up letter will be completed approximately two weeks after the routine monitoring visit; a copy will be maintained in the study file. The monitor will request additional source documentation, clarification, information, or corrections to the CRF and/or regulatory records from the Clinical Research Coordinator (CRC) or other applicable staff responsible for the study and resolution of queries/findings. Documentation of such a request will be maintained with a copy of the monitor's visit report for follow-up at the next monitoring visit. Electronic records will be available in the institutional database or provided by the CQA Program staff.

All monitoring reports must be completed and submitted to the local site PI, the Sponsor-Investigator, and UACC DSMB. All submitted serious adverse events will be submitted to the UACC DSMB Coordinator monthly and then reviewed by the DSMB Chair. Any identified SAE trends will be made available for review at the investigator teleconferences.

A teleconference will occur on a regular schedule to review study progress and any safety, or other, issues. Minutes of these teleconference meetings will be submitted to UACC DSMB for review.

At each site, the Principal Investigator will ensure the accuracy, completeness, legibility and timeliness of the data reported in the OnCore electronic Case Report Form (eCRF), and other data formats. Source documentation supporting the study data should indicate the subject's participation in the trial and should document the dates and details of study procedures, adverse events, and patient status.

Case report forms, which include adverse event forms, serious adverse event forms, and protocol or patient deviations must be completed via the RedCap database

9.4 Plan for assuring data accuracy and protocol compliance:

Any identified safety issue will be submitted to the UA IRB, DSMB or other oversight entity as applicable. Each month the DSMB will perform a review of study activity and safety information at each site. A summary of activity at all sites will be reviewed including the following:

- Study activity, cumulative and for the period under review;
- Safety information (non-serious and serious adverse events);
- Status of study in relationship to stopping rules;
- Routine monitoring and protocol compliance (describe the monitoring process and identify the status of the monitoring);

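### The toxicity rule is described as continuous but starts after the 6th enrolment, although its own 50% posterior limit is already met at 4 of 4 and 5 of 5 discontinuations

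*Combined protocol and SAP*

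**What the plan says.** Sections 5.2 and 10.3.1 both introduce the rule in the same terms: "A continuous monitoring rule for safety will be instituted, to guard against excess toxicity". Section 10.3.1 then sets one criterion. If the posterior probability of a discontinuation rate of at least 33% exceeds 50% "for patients having to discontinue window treatment due to qualifying toxicity, this would be considered unacceptable", the study goes on hold and is referred to the safety board. The prior is Beta(1,9), with mean 10%.

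The criterion is stated without a minimum number of patients. The start of monitoring is stated separately: "After enrollment of the 6th patient, we will continuously monitor the number of patients who discontinue BYL719". Table 8 agrees with that start. Its first row is 5 discontinuations in 6 subjects, with posterior .629, and there is no row below 6. No reason is given for waiting until the sixth patient.

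Other oversight runs from the first patient. Section 8.4 has the safety board meet every four weeks and review grade 3 to 5 events. Section 8.5 requires serious adverse events to be reported within 24 hours. Section 9.4 says "Each month the DSMB will perform a review of study activity and safety information at each site", and its list of items includes "Status of study in relationship to stopping rules". Section 10.3.2 stops enrolment if more than 3 of the first 14 patients have an unacceptable, drug-related delay in surgery.

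**The concern.** The criterion and the start point do not match. If the first four patients all stop the drug for qualifying toxicity, the posterior is .562 and the plan's own test calls the rate unacceptable. The rule is not yet active, so a fifth and a sixth patient can be enrolled without a hold. At 5 of 5 the posterior is .699, higher than any value in Table 8 (the largest is .685, at 6 of 8), yet no hold applies until one more patient has been enrolled.

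At stake is the exposure of one or two further patients, all awaiting potentially curative surgery, after the plan's own limit has been passed. The informative prior already damps early false alarms (1 of 1 gives .108 and 2 of 2 gives .241), so it is unclear what the waiting period adds.

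**Working it through.** **Inputs, all from Section 10.3.1.** Prior Beta(1,9); rate 0.33; posterior limit 0.50; first look at 6 subjects; maximum 20 subjects.

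**Formula.** With r discontinuations in n patients, the posterior is Beta(1+r, 9+n−r). Its upper tail at 0.33 equals P(Y ≤ r), where Y is binomial with 9+n trials and probability 0.33.

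**Step 1: reproduce Table 8.**

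| Discontinued / treated | Table 8 posterior | Recomputed |
|---|---|---|
| 5/6 | .629 | .629 |
| 6/8 | .685 | .685 |
| 7/11 | .673 | .673 |
| 8/14 | .664 | .664 |
| 9/17 | .657 | .657 |
| 10/20 | .650 | .650 |

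All six rows agree, so the model used here is the plan's own.

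**Step 2: apply the same formula before the sixth patient.**

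| Discontinued / treated | Posterior | Above .50? |
|---|---|---|
| 1/1 | .108 | no |
| 2/2 | .241 | no |
| 3/3 | .403 | no |
| 4/4 | .562 | yes |
| 4/5 | .486 | no |
| 5/5 | .699 | yes |

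Only 4/4 and 5/5 cross. With 1/3 in place of 0.33 they become .552 and .690, so the conclusion is unchanged.

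**Step 3: what happens next under the plan as written.**
- After 5/5, the sixth patient brings the count to at least 5/6 (.629). The hold follows, one enrolment late.
- After 4/4, at least one event in the next two patients gives at least 5/6 and a hold. If neither has an event, the first look is 4/6 (.415) and there is no hold at that point.
- From 4/6, an event in patient 7 gives 5/7 (.558) and a hold. The exact chance of a hold between patients 7 and 20, starting from 4/6, is 67% at a true rate of 33% and 93.5% at 50%.

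**Step 4: size of the gain.** With a start at patient 1, the chance of a hold by patient 4 is p⁴, where p is the true rate: 0.5⁴ = 6% and 0.7⁴ = 24%. It is now zero. By patient 6 the two versions differ only by the path 4/4 followed by two patients without an event, which has probability p⁴(1−p)²: .0625 × .25 = 1.6 points at 50%, and .2401 × .09 = 2.2 points at 70%. An exact patient-by-patient recursion gives the cumulative chance of a hold:

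| True rate | By patient 6: start at 6 | By patient 6: start at 1 | By patient 20: start at 6 | By patient 20: start at 1 |
|---|---|---|---|---|
| 33% | 1.7% | 2.2% | 19.2% | 19.4% |
| 50% | 10.9% | 12.5% | 72.5% | 72.6% |
| 70% | 42.0% | 44.2% | 99.2% | 99.2% |

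At a true rate of 10%, the figure by patient 20 stays below 0.1% either way.

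**The case against.** The strongest reply is that the start at 6 is a visible design choice. The text and Table 8 agree on it, a minimum number before a first look is common, and patients 1 to 5 are not unmonitored. The safety board meets every four weeks, serious events are reported within 24 hours, and four surgery delays in four patients would trigger Section 10.3.2. Section 11.7 also allows suspension for unacceptable risk. Accrual of 20 patients over 24 to 64 months averages about 1.2 to 3.2 months per patient (24/20 and 64/20), so a board meeting would usually fall between consecutive enrolments. All of this stands and limits the weight of the point. None of these safeguards applies the posterior trigger or its automatic hold, and the plan does not explain why its criterion is suspended for the first five patients.

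Three stronger readings are tempting, and the documents do not support them.
- A reader might infer that early events are ignored. They are not: they count in full at the sixth patient, and 5 of 5 is always caught there.
- A reader might infer that a study at 4 of 4 and then 4 of 6 escapes for good. It does not: one event in patient 7 meets the criterion.
- A reader might take the 6% and 24% at patient 4 as lasting gains in detection. Most of that gain is gone by patient 6 and almost all of it by patient 20.

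**Conclusion.** The point holds as a small one. The plan's 50% posterior criterion is met at 4 of 4 and 5 of 5, and the start after the sixth enrolment delays action by one enrolment at 5 of 5 and by up to two at 4 of 4. In the single path of 4 of 4 followed by two patients without an event, the crossing passes without a hold at that time. That path has probability 1.6% at a true 50% rate and 2.2% at 70%. The benefit of a change is earlier action in a rare, extreme sequence; overall operating characteristics barely move.

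The probabilities assume independent patients with a common discontinuation rate, each outcome known before the next enrolment, and a recursion that ends at the first hold. The true rates of 33%, 50% and 70% are illustrative. The posterior values need none of these true rates, only the plan's prior and its 0.33 cut-off.

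**What to change.** Reconcile the start point with the criterion. The direct way is to remove the condition on the sixth enrolment, apply the existing posterior rule from the first treated patient, and add one row to Table 8: 4 subjects, 4 discontinuations, posterior .562, binomial probability .012 (0.33⁴). A footnote should say that 4 of 5 (.486) does not meet the criterion, so that the new row is not carried forward to five subjects. A row for 5 of 5 would matter only if the study resumed after a hold at 4 of 4. No new threshold is introduced.

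If the delay is intended, one sentence should say why the criterion does not apply before the sixth patient and who acts on 4 of 4 in the meantime.

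The cost is one phrase, one table row and a footnote, and about 0.2 percentage points more chance of a hold by patient 20 at a true 33% rate (19.2% to 19.4%).
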